1.0 PURPOSE

1.1 Name and Intended Use

The purpose of this study is to evaluate histological results of the treatments with the TempSure Firm handpiece on the flanks performed in the CYN20-FIRM-LIPO study.

1.2 Objectives

Primary Objective:

- Evaluate histological tissue response as seen in biopsies.

1.3 Duration of the Investigation

The sponsor anticipates that all subjects can be enrolled within 3 months. If subject participates in all required visits, then the subject's participation in this study may last up to 1 month. It is anticipated that it will take approximately 3 months to analyze the data collected during this study. The total duration of this study is anticipated to last approximately 7 months.

1.4 Context of the Proposed Investigation

Radiofrequency (RF) technology is commonly used in surgery, noninvasive treatments and aesthetic applications. RF technology is a safe method for non-ablative (A non-wounding device treatment which heats underlying skin) treatment because energy can be precisely delivered through the skin to the dermal tissue beneath without damaging the epidermis.

Aging skin shows decreased collagen synthesis and alteration of fiber networks. By gently heating dermis tissue (which is comprised of collagen, elastic fibers and ground substance), both immediate effects (collagen contraction) and long-term effects (wound-healing response with neocollagen production) will occur. RF-induced thermal injury to the dermal tissue will produce a microinflammatory response to induce collagen denaturation, contraction, and subsequent synthesis as well as elastin and ground substance production.¹ This, in turn, creates a tightening effect that helps to eliminate skin wrinkles and is used also for other cosmetic treatments on the body.²

The extent of collagen shrinkage, fibroblast activation, fibroplasia and neocollagenesis in the different skin layers is based on a complex multivariate mechanism, which depends on the temperature distribution and timing.² Further investigation of parameter optimization is necessary to achieve safe and efficacious results.

2.0 PROTOCOL

2.1 Protocol Methodology and Analysis

Methodology:

Subjects are to be enrolled in this clinical study if they have completed their participation in the CYN20-FIRM-LIPO study. Up to 10 subjects will be enrolled at up to 4 study centers. Subjects will receive 2 biopsies, 1 biopsy in the treatment area on the flank and 1 biopsy on the contralateral side to serve as a control.

Analysis:

Upcoming generations are proving to have an interest in non-ablative aesthetic treatments and will drive demand for innovated products, procedures, and practice design.³ Due to this shift in patient base, practices need to evolve to adapt to the newer generational ideologies. There have been rapid advances in RF technology over the past few years and the nonsurgical treatment using this energy source offers great promise to our aging population.⁴ Radiofrequency technology for the treatment of abdominal wrinkles needs to be further investigated to optimize treatment parameters for safe and effective non-ablative aesthetic treatments.

Relevance:

Over time, skin structure degrades due to a variety of internal and external conditions. As enzymes break down collagen and elastin, skin loses its suppleness and becomes loose. UV exposure, diet, and smoking among other behaviors all contribute to the skin becoming lax. Body wrinkles, particularly on the abdomen, are a sign of aging and are also a prevalent concern with postpartum women or subjects who have lost weight. It is estimated that adult skin loses approximately 1% of its dermal collagen content on an annual basis due to increased collagen degradation and decreased collagen synthesis.² Radiofrequency, ultrasound, non-ablative fractional technology, and ablative technology have all been used to varying degrees of success. The limitations of current products on the market include different side effect profiles and modes of administration.

Testability:

The improvement in the appearance of skin has been previously linked to a histological evaluation of the treatment area and can be used to verify an increase in collagen after a radiofrequency treatment. [name] in 2008 published an article titled *Tissue Tightening Technologies: Fact or Fiction* which discusses the link between changes in collagen and improvement in skin tightening, including wrinkles. The collection of biopsies will allow a histological evaluation of the treatment area to confirm the device is safely and effectively affecting the collagen in the dermis.

Compatibility:

Not applicable – feasibility study.

Predictive power:

While this study will observe the effects of the handpieces on the flanks, results could potentially be applied to a variety of body areas and other potential applications. Assuming that there is significant improvement, it would be appropriate to expect results in different areas where other products and devices have significant results.

2.2 Protocol Study Design

This is a prospective, multi-center clinical study to evaluate histological results of treatments with the TempSure™ Firm handpiece.

2.3 Subject Selection Criteria

Subjects will meet the criteria described below:

Inclusion Criteria:

- Subject has completed their participation in the CYN20-FIRM-LIPO study no more than 6 months prior.

Exclusion Criteria:

- The subject has not had any other treatment in the treatment area after their involvement in the CYN20-FIRM-LIPO study.
- The subject has any condition or is in a situation which in the investigators opinion may put the subject at significant risk, may confound study results or may interfere significantly with the subject's participation.

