2.5 Informed Consent Process and Enrollment

Subjects will be asked to review the post treatment instructions prior to signing the informed consent form and their involvement in the study. Subjects will be informed of standard COVID-19 procedures that adhere to federal and state guidelines at this time. Subjects will be de-identified through their subject identification number, which will be stored in a secure location. Subject identification numbers will be generated chronologically and assigned only to subjects who have met all the study selection criteria and have signed the informed consent form. The informed consent will be obtained prior to a subject's involvement in any study related procedures. A subject will be considered enrolled in the study once they have signed the informed consent form.

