12.0 PROTOCOL DEVIATIONS

All requests for protocol deviations by the Investigator have to be communicated to the sponsor in writing and if accepted by the Sponsor must be approved by the IRB. If a deviation occurs, the Investigator must inform the Sponsor as soon as possible. The Sponsor will notify the IRB in accordance with IRB specific policies.

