18.0 PROCEDURE FOR AMMENDMENTS TO PROTOCOL

No deviations from this protocol will be permitted, except in a medical emergency, without the approval of the Sponsor. Any amendment to this study will be discussed by the Investigator and the Sponsor. If agreement is reached concerning the need for modification, this will be made in a formal amendment to the protocol.

All revisions and/or amendments to the protocol must be approved in writing by the appropriate Institutional Review Board.

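### The first exclusion criterion is inverted: it bars subjects with no later treatment in the treatment area and lets through those who had one

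*Protocol*

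**What the plan says.** Section 2.3 opens both lists with one lead-in: "Subjects will meet the criteria described below". The single inclusion criterion requires completion of CYN20-FIRM-LIPO within the previous 6 months and is silent on later treatments. Two exclusion criteria follow.

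- First: "The subject has not had any other treatment in the treatment area after their involvement in the CYN20-FIRM-LIPO study".
- Second: any condition or situation that "in the investigators opinion may put the subject at significant risk, may confound study results", or that may interfere with participation.

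Other sections bear on how these criteria work:

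- Section 1.1 gives the purpose: to "evaluate histological results of the treatments with the TempSure Firm handpiece on the flanks performed in the CYN20-FIRM-LIPO study".
- Section 2.1 sets the size: "Up to 10 subjects will be enrolled at up to 4 study centers". Each subject gives one biopsy from the treated flank and one from the contralateral side as control.
- Section 2.5 says subject numbers are "assigned only to subjects who have met all the study selection criteria and have signed the informed consent form".
- Section 18.0 states: "No deviations from this protocol will be permitted, except in a medical emergency, without the approval of the Sponsor".
- Section 12.0 says a deviation request "if accepted by the Sponsor must be approved by the IRB".

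**The concern.** The first exclusion criterion is worded as a condition that a suitable subject should satisfy, yet it stands in the list of conditions that rule a subject out. Taken at its word, it turns away the people the study wants and admits those it should keep out.

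This matters because the study rests on a within-subject comparison of a treated site with a contralateral control. Another treatment applied to the treated area after CYN20-FIRM-LIPO would alter one side of that comparison, and its effect on collagen and elastin could not be separated from that of the TempSure Firm treatments. This bullet is the only rule aimed specifically at that problem.

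Even if every site reads through the error, the written criterion still governs. Subjects enrolled as intended would fail the eligibility rule as printed.

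**Working it through.** The protocol gives no figure to reproduce on this point. The check is one of logic and of setting the sections side by side.

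**Definitions.** Let T mean that the subject had another treatment in the treatment area after CYN20-FIRM-LIPO. Let C mean that the investigator judges the subject's situation to be confounding under the second exclusion bullet. Assume that the inclusion criterion is met and that nothing else in the second bullet applies.

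**Eligibility as written.** The first bullet excludes when T is false and the second excludes when C is true. So eligible = NOT(NOT T) AND NOT C = T AND NOT C.

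**Eligibility with *not* deleted.** The first bullet excludes when T is true. So eligible = NOT T AND NOT C.

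| Later treatment (T) | Judged confounding (C) | Eligible as written | Eligible with *not* deleted |
|---|---|---|---|
| No | No | No | Yes |
| No | Yes | No | No |
| Yes | No | Yes | No |
| Yes | Yes | No | No |

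As written, 1 of the 4 combinations is eligible, and it is not the intended one. If investigators judged every later treatment in the area confounding, the third row would be empty and no one would be eligible. These are logical cases, not proportions of subjects. The protocol gives no frequency for either T or C.

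**Can the lead-in rescue the list?** Suppose it means that every listed statement must be true of every subject. The first bullet then says what was intended. The second would require each subject to have a condition that raises risk, may confound the results or may interfere with participation, which is absurd. The two bullets have opposite polarity under one heading, so no single reading makes both sensible.

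**Is it corrected elsewhere?** Section 2.4 only points to the screening in the parent study, which cannot cover treatments received afterwards. The revisions tracker in Appendix A records the added 6-month limit in the inclusion criteria and no change to this bullet.

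**Size of the consequence.**

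- Sites follow the intent: every enrolled subject meets a written exclusion criterion, which is up to 10 of 10 at full enrolment.
- Sites follow the text: every enrolled subject has had another treatment in the treatment area, again up to 10 of 10.
- A site admits one such subject: with one biopsy pair per subject, that is 1/10 = 10% of the pairs at full enrolment, and a larger share if fewer enrol.

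**The case against.** The strongest reply is that this is a one-word slip whose meaning nobody would mistake. The purpose makes the intent obvious, the shared lead-in lends some support to reading the bullet as a condition to be met, and sites would almost certainly apply it that way. The second bullet also lets the investigator keep out anyone whose situation may confound the results, and a later treatment in the biopsied area fits that description. On this view no bias is to be expected and the point is editorial.

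Much of this is fair. The realistic consequence is formal, and the second bullet gives some protection. But that protection depends on individual judgement across up to 4 centers, and it cannot make eligible again the untreated subjects whom the first bullet rules out.

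Three narrower points also stand:

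- Section 1.1 states an aim and not an eligibility rule, so the criterion conflicts with the purpose but does not formally contradict it. The two exclusion bullets can also be applied together; they simply select the wrong subjects.
- Section 2.5 treats a subject as enrolled on signing consent, so the barrier there concerns the subject number and not enrolment itself.
- Section 12.0 has a second route, for deviations that have already occurred: the investigator informs the sponsor, who notifies the IRB under its policies.

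None of these removes the inversion.

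**Conclusion.** The concern holds. The criterion says the opposite of what the study needs, no consistent reading of Section 2.3 repairs it, and no other section corrects it.

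The conclusion rests on the ordinary meaning of an exclusion criterion and on the stated purpose. It needs no assumption about how often later treatments occur. The likely harm is to compliance and not to the data: enrolling the intended subjects departs from the written protocol, which outside a medical emergency needs the sponsor's approval under Section 18.0, with IRB approval of an accepted request under Section 12.0. Damage to the histological comparison would follow only if a site applied the text literally or let through a subject with a later treatment.

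It should still be corrected before enrolment. This is an operative eligibility rule, which belongs in the protocol and which a statistical analysis plan would not put right.

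**What to change.** Delete *not* from the first exclusion criterion, so that a subject who has had any other treatment in the treatment area since CYN20-FIRM-LIPO is excluded. Alternatively, move the sentence unchanged to the inclusion list. Either change gives the intended rule; making both would invert it again.

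Confirm the absence of later treatment in the eligibility check that Section 2.5 already implies, before the biopsies are taken.

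The cost is a one-word or one-sentence formal amendment with written IRB approval, as Section 18.0 requires. No subjects, visits or procedures are added.

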2.4 Screening

Subjects will undergo the screening procedures in the CYN20-FIRM-LIPO study.

2.5 Informed Consent Process and Enrollment

Subjects will be asked to review the post treatment instructions prior to signing the informed consent form and their involvement in the study. Subjects will be informed of standard COVID-19 procedures that adhere to federal and state guidelines at this time. Subjects will be de-identified through their subject identification number, which will be stored in a secure location. Subject identification numbers will be generated chronologically and assigned only to subjects who have met all the study selection criteria and have signed the informed consent form. The informed consent will be obtained prior to a subject's involvement in any study related procedures. A subject will be considered enrolled in the study once they have signed the informed consent form.

2.6 Pre-Biopsy Procedures

If the subject is of childbearing potential (i.e. females not post-menopausal or not surgically sterile), they will be asked if they are pregnant, the date of their last menstrual cycle, and perform a urine pregnancy test. A urine pregnancy test will be performed on all women of childbearing potential prior their biopsies. A urine pregnancy test may also be conducted at the Investigator's discretion at any time during the study. If a urine pregnancy test is conducted, then a negative result must be obtained within 24 hours prior to the treatment.

Urine Pregnancy Test Procedure:

1. A urine sample is tested mid-stream or by cup sample with an indicator stick.
2. Negative results are indicated on the indicator stick.

- The biopsy area will be identified and may be marked with a surgical or permanent marker.
- Photographs will be taken prior to the biopsy and may be taken during and/or after treatment.

2.7 Biopsy Procedures

- Biopsy subjects will receive 2 biopsies, 1 in the treatment area and 1 on the contralateral side of the treatment area to serve as a control.
- A local anesthetic, such as lidocaine, will be injected to the area prior to biopsy.
- A 2 mm or 3mm punch biopsy (based on Physician assessment) will be taken.

- Sutures may be used to close the incision site.

2.8 Post Biopsy Instructions

- Slight redness, initial tenderness to the wound site is normal; however, if you experience more redness, swelling, pain, pus, or drainage contact the office immediately,
- If the biopsy site begins to bleed, apply direct pressure for 10-20 minutes. If it continues to bleed, call the study site immediately.
- Keep the wound dry today and remove bandage in 24 hours and leave off.
- Avoid hot tubs, pools, and ocean until sutures are removed. Avoid soaking in water until 14 days after your biopsy.
- When showering, wash carefully and do not scrub or traumatize the treated skin, or allow spray of shower to strike the skin directly. If the skin is treated harshly, this can increase the risk of scarring.
- After showering, lightly pat dry the wound or let it air dry, then cover the biopsy site with an application of Vaseline (or petroleum jelly) at least 1-2 times daily. Keeping the wound moist reduces infection, minimizes scarring, and prevents crust formation over the wound.
- Band-Aids (or any generic Adhesive Bandages) may be used for sleeping or in daily routines where the area may be rubbed/irritated. Whenever possible, keep Band-Aid (or generic Adhesive Bandage) off of the area and keep the area moist with Vaseline (or petroleum jelly) as previously described but do not allow drying out and forming a hard scab.
- For any wound discomfort, you may take Tylenol as needed, or use cold compresses for up to 20 minutes hourly as needed. If using ice, it should be wrapped in a plastic and then a cloth to avoid burning your skin and wetting your bandage.
- Avoid picking at the wound site, which increases risk of infection and scarring.
 - In order for the wound to heal properly and not leave bumpy scars, be careful not to overstretch the wound site area. As a wound heals, it will be weaker than the surrounding skin and can even "pop open" the sutures (stitches) if stretched too much. Sport or strenuous exercises that can pull at the wound site are best avoided for at least the next 3 days and up to one week.
- Return for suture removal within 7 - 10 days as instructed per study protocol. If applied, Steri-strips must be kept dry as they are more likely to separate when wet. Steri-strips will usually fall off by themselves or you may be advised by the study doctor to remove them when the wound healed.
- ONCE SUTURES ARE OUT: To minimize sore formation and to improve the final appearance of your skin, it is very important to keep the wound site area covered with the Vaseline for the next few days, until there is no more crust forming and the skin has completely healed.
- Temporary discoloration at the wound site is normal and should gradually fade over the next few months. Please protect newly healed biopsied area with SPF and avoid sunburn.

2.9 Follow Up

- The subject may be asked to attend a 1 week (7-10 days) post biopsy follow up visit to remove the sutures.

- Photographs may be taken, and adverse events will be documented at this follow up visit.

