2.12 Schedule of Visits and Procedures

	Visit #1	Visit #2 (optional)
Procedure	Biopsy	Follow Up 1 Week Post Biopsy (7-10 Days)
Pregnancy Verification*	X	
Biopsy	X	
Suture Removal		X
Photographs	X	X
Adverse Events Assessment	X	X

*Pregnancy verification required before biopsy only for women of childbearing potential.

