2.14 Adverse Event Recording

All data captured must be supported by the Investigator's timely assessment and documentation of the adverse event in the case report forms or source documents. All documented adverse events will be reviewed by the Sponsor or designee to determine whether the adverse event meets

regulatory reporting requirements and to ensure timely adverse event reporting to meet local and global regulatory requirements. All adverse events must be followed until their resolution.

Biopsies

Complication with biopsies can include pain, redness, swelling, infection, bleeding, scarring and skin texture irregularities.

Lidocaine

1% lidocaine (Lidocaine) Injection with or without Epinephrine

You may experience pain and numbness at the site of the injection. You may also experience redness, rash, infection, skin damage or nerve damage at the site of the injection. You may experience temporary loss of sensation and muscle function at the site of injection.

Lidocaine with epinephrine contains the preservative sodium metabisulfite which may cause allergic-type reactions including anaphylactic symptoms and life-threatening or less severe asthmatic episodes in certain susceptible people.

Adverse Events Pertaining to Surgical Marker:

Using surgical marker has minimal risks and may produce effects on the body such as redness or a rash. Markings may remain visible for a few days or may be removed with alcohol.

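### The only scheduled adverse-event assessment after biopsy day is an optional suture-removal visit, so a subject without sutures, or one not asked back, has none

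*Protocol*

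**What the plan says.** - **Schedule (Protocol 2.12).** Two visits are listed. The second is headed "Visit #2 (optional" and falls 7-10 days after the biopsy. Adverse-event assessment is marked at both visits and at no other time.
- **Follow-up (Protocol 2.9).** "The subject may be asked to attend a 1 week (7-10 days) post biopsy follow up visit to remove the sutures". The recording of events is attached to that visit: "Photographs may be taken, and adverse events will be documented at this follow up visit".
- **Wound closure (Protocol 2.7).** "Sutures may be used to close the incision site".
- **Instructions to subjects (Protocol 2.8).** "Return for suture removal within 7 - 10 days as instructed per study protocol". Subjects are also told to contact the office if the wound worsens.
- **Expected complications (Protocol 2.14).** "Complication with biopsies can include pain, redness, swelling, infection, bleeding, scarring and skin texture irregularities". No onset times are given.
- **Other routes.** Section 2.10 allows an unscheduled visit at the subject's request or on the investigator's judgment. Section 11.0 lets subjects contact the investigator at any time, and states that adverse events are captured for the duration of the study and that known events are followed up.

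**The concern.** Section 11.0 promises capture of adverse events over the whole study, but the schedule contains no contact after biopsy day that every subject must have. The one later assessment sits inside a visit whose stated purpose is removing sutures, and some subjects may have no sutures to remove. Whether anyone asks a subject about adverse events after biopsy day then depends on how the wound was closed and on whether the site chose to ask the subject back.

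At stake is the meaning of the adverse-event listing. Each subject has two punch biopsies, one on each flank. If some subjects are asked about these sites a week later and others are not, the listing mixes two levels of observation. For a subject with no later contact, an empty record could mean that nothing happened or that nobody asked. With up to 4 centers, closure and call-back habits may also differ between sites.

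**Working it through.** The protocol states no figure on this point to reproduce, so the check is to set the sections side by side and count.

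**Inputs.** Up to 10 subjects, 2 biopsies each and up to 4 centers (2.1); two visits, the second optional (2.12); attendance on request (2.9); sutures discretionary (2.7).

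**Step 1. Scheduled adverse-event assessments per subject.**

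| Subject | Visit 1 | Visit 2 | Scheduled after biopsy day |
|---|---|---|---|
| Sutured, attends Visit 2 | yes | yes | 1 |
| Sutured, not asked back under 2.9 | yes | no | 0 |
| Unsutured, asked back and attends | yes | yes | 1 |
| Unsutured, not asked back | yes | no | 0 |

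The second row is the less likely one, because 2.8 tells subjects to come back for suture removal. The fourth row meets no such instruction, so the gap falls mainly on unsutured subjects.

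**Step 2. What the schedule guarantees.** Guaranteed scheduled assessments after biopsy day: 0 of up to 10 subjects. The most the schedule can deliver is 10 of 10. The biopsy sites concerned number up to 10 × 2 = 20. The documents do not say how many subjects are expected to have sutures, so the likely position between these limits cannot be calculated.

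**Step 3. Whether another provision fills the gap.**
- The contact instructions in 2.8 and 11.0 depend on the subject speaking up.
- The unscheduled visit in 2.10 depends on a request or on the investigator seeing a need.
- The capture statement in 11.0 is a duty on the site, but no contact is attached to it.
- The requirement in 2.14 and 11.0 to follow events applies to events already known.
- Section 9.0 asks withdrawing subjects to a final follow-up visit. No such visit is stated for an unsutured subject who completes the study.

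None of these produces a dated entry that a subject was asked and had no event.

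**Step 4. Whether the sections agree.** Section 2.8 points to a protocol instruction to return for suture removal, whereas 2.9 and 2.12 leave the return open. The two can be read together as a visit for those with sutures, but neither 2.9 nor 2.12 says so.

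**The case against.** The strongest reply is that the protocol does not leave these subjects unobserved. Adverse events are assessed at Visit 1, sutured subjects are told to return, all subjects are told when to call, investigators may arrange a visit, and Section 11.0 imposes a duty for the whole study. A site that closed its adverse-event record on biopsy day would arguably breach that duty. Nor are these routes all self-report, since 2.10 includes the investigator's own judgment. All of this stands, and it limits the point to scheduled assessment. It does not supply a planned contact.

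A reader might also infer more than the documents support:

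- **That most listed complications cannot be seen on biopsy day.** Section 2.14 lists seven and gives no onset time for any. Infection, scarring and texture change plausibly come later, but that is an inference, and it concerns three of the seven.
- **That subjects not seen again would be counted as free of events.** The protocol states no such counting rule.
- **That follow-up must run to one month or beyond.** Section 1.3 says only "then the subject's participation in this study may last up to 1 month", which is a ceiling. The remark in 2.8, "Temporary discoloration at the wound site is normal and should gradually fade over the next few months", is aftercare advice about a change described as normal. Neither calls for a later contact.
- **That the study fails to estimate a complication rate.** The only objective in 1.2 is histological. No safety rate or hypothesis is stated, so there is no target against which to judge precision.

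**Conclusion.** The point holds for scheduled assessment. A site can keep to 2.7, 2.9 and 2.12 and have no planned adverse-event check after biopsy day for an unsutured subject, or for one not asked back. In the extreme this covers all of the up to 10 subjects. The actual number depends on suture use and site practice, which the documents do not fix. The consequence is uneven ascertainment, and records in which no report and no event look alike.

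This is a modest weakness in safety data collection. It does not touch the histological endpoint, and it does not show that any event would in fact be missed. The conclusion rests on the visit schedule being the full list of planned contacts; nothing else in the protocol describes another one for subjects who complete the study.

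**What to change.** In 2.9 and 2.12, separate the adverse-event assessment from suture removal. Make the assessment required for every biopsied subject within the existing 7-10 day window: in person if a visit takes place, otherwise by a scripted telephone call that asks about each complication listed in 2.14 at both biopsy sites. Record the date and the answer, including a negative answer.

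Reconcile 2.7, 2.8, 2.9, 2.12 and 11.0 so that they agree on who returns and on how adverse-event status is obtained for those who do not. Which subjects return for suture removal is for the sponsor and investigators to settle; the sections only need to say the same thing.

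The cost is a change of wording, one row in the schedule and at most 10 × 1 = 10 short calls. No procedure or subject is added. The downside is a little site time and possibly more minor events on record. A call cannot examine the skin, but it does establish that the subject was asked.
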